The FS-ICU was initially developed and validated in a single hospital setting in Ontario, Canada,⁶ and subsequently validated in a multicentre study in six sites across Canada.⁷ Further studies have addressed the face/content, construct, sensitivity and responsiveness of the instrument.⁸ In 2007, it underwent further refinement, including reduction of the number of items from 34 to 24 by identifying items with poor response, poor discrimination (floor/ceiling effects), redundancy (high Cronbach's α) and those measuring another construct (identified by principal component analysis).

The 24 item version increases its feasibility for future administration and performs well in head-to-head comparisons with other measures of ICU quality.⁸

It is widely acknowledged that cultural and linguistic differences between, and even within, countries mean that an instrument developed and validated in one place cannot simply be used in another without careful cross-cultural adaptation and checking of psychometric properties. The most common approach to developing cross-cultural instruments is the sequential approach,⁹ in which an instrument is initially developed and the psychometric properties are validated in one culture; it is subsequently translated (if necessary) and the properties re-established in other cultures. This approach is exemplified by the International Quality of Life Assessment project, which produced cross-cultural adaptations of the SF-36.¹⁰ By showing that minimum standards (e.g. application of recognised criterion values, replication of original factor structures and tests of discriminant validity) are met across a range of cross-cultural adaptations, and that performance in a new adaptation is similar to that of the original version, one can have greater confidence that the instrument can be considered to have international applicability.¹⁰ The SF-36 has been established as a valid measure for use in the UK following cross-cultural validation and extensive psychometric testing^{11;12} and population norms have been derived from large cohorts.¹³

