The overall aim of the FREE Study is to inform valid, representative and cost-effective future use of the FS-ICU questionnaire into quality improvement programmes for adult critical care services in the NHS in the UK.

The objectives of the FREE Study are:

- to test the face and content validity and the comprehensibility of the FS-ICU;
- to establish the internal consistency, construct validity and reliability of the FS-ICU;
- to describe family satisfaction using the FS-ICU and explore how family satisfaction, measured with the FS-ICU, varies by:
 - family member;
 - patient characteristics;
 - unit/hospital characteristics;
 - other contextual factors; and
 - country (through comparison with FS-ICU data held in Canada);
- to model approaches to sampling to achieve representative sampling for feasible, cost effective future use of the FS-ICU in quality improvement in the NHS.

4. Study design

The FREE Study is a mixed methods study comprising a psychometric evaluation (FREE-Qual) leading to a multicentre cohort study.

The objectives of the FREE Study will be addressed in two sub-studies.

FREE-Qual

FREE-Qual is a qualitative study (see: Section 5) which will address the first objective by testing the face and content validity and the comprehensibility of the validated Canadian FS-ICU. Modifications to the FS-ICU questionnaire will then be made, if required.

The FREE Study

FREE is a multicentre cohort study (see: Section 6) which will address the remaining objectives using the UK adaptation of the FS-ICU questionnaire (FREE-Qual).

Staff at twenty adult, general critical care units will identify up to four family members for consecutive patients admitted to their unit who stay more than 24 hours. Family members who consent to take part will be sent a questionnaire three weeks following patient discharge from the critical care unit.

The recruitment period will be one year, chosen to avoid bias from seasonal variation in case mix and workload. A psychometric assessment of the FS-ICU will be undertaken using data collected during the first month.

5. FREE-Qual

Research Ethics Committee reference:	12/YH/0415
Sponsor reference:	ICNARC/02/05/12
NIHR CRN Portfolio ID number:	112459
Protocol version:	1.0
Protocol version date:	31 July 2012

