5.2 Study design

5.2.1 "Translation" of FS-ICU questionnaire

The FS-ICU uses North American English. The research team will review the questionnaire and render into UK English any words or items that require 'translation' (e.g. 'junior doctor' for 'resident'). [name], the developer of the FS-ICU, will advise on whether semantic equivalence has been maintained.

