5.2.3. Focus Groups

A series of 3 focus groups will be undertaken facilitated by the Research Associate.

Two focus groups will be undertaken with multidisciplinary teams of healthcare professionals involved in the delivery of critical care to further inform whether the FS-ICU covers all dimensions they consider relevant, from a family member's perspective, to the quality of critical care (and on which a family member could be expected to have a view). The groups will be representative of the multidisciplinary critical care team – including doctors, nurses, and physiotherapists – and will be selected and conducted in two different geographical regions, the North East of England and London. At the end of a free-ranging discussion, the healthcare professionals will be presented with the FS-ICU and will be asked to comment on the relevance and redundancy of items. Focus group discussions will be recorded, transcribed and thematically analysed. This will provide a further perspective on face and content validity of the FS-ICU.

A third focus group will be undertaken with representatives from the charity ICUsteps (The Intensive Care Unit Support Teams for Ex-Patients, Registered Charity No. 1117033.) This support group, which was founded in 2005 by ex-patients, their relatives and ICU staff, will provide the final perspective on the face and content validity of the FS-ICU. The methods will mirror those for the healthcare professional focus groups.

If findings from the cognitive interviews or focus groups suggest that one or more items from the FS-ICU should be dropped, this will be discussed with [name] and the rationale for deletion or retention recorded. Similarly, if additional content is suggested by family members, healthcare professionals, or representatives from ICUsteps, appropriate items (with the same response format as existing FS-ICU items) will be drafted and tested through further cognitive interviews with family members.

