7.2 Statistical analysis

Psychometric assessment

Once completed questionnaires have been returned from family members recruited during the first month of recruitment (approximately 1000) and the data entered onto a secure database at the ICNARC CTU, a psychometric assessment of the FS-ICU will be rapidly undertaken. If results from the psychometric assessment demand substantive changes to the FS-ICU questionnaire, then these will be incorporated into a new version of the FS-ICU questionnaire and recruitment and data collection will re-commence and continue for 12 months.

The methods used in the psychometric assessment will mirror those employed in the North American validation study⁸ and utilise their FS-ICU scoring algorithm. The analysis will comprise the following steps: descriptive analysis; item reduction; factor analysis; reliability analysis; and validity analysis. Brief methods for each step are outlined below.

Descriptive analysis

Item descriptive statistics (percentage missing, percentage floor/ceiling scores, frequencies, median and interquartile range) will be computed for each site and all sites combined.

¹ FREE is recruiting family members for all patients staying 24 hours or more, however for the purpose of estimating targets we have excluded patients staying less than 36 hours - given family members of short term patients may not visit before discharge from critical care

Item reduction

In adapting an existing validated measure for use in another culture, there is a tension between the desirability of keeping the instrument in its previously validated form and the need to ensure scale integrity, which might require dropping poorly performing items. The following criteria will be used to tag items for possible removal:

- items with high item non-response rates (>10%), suggesting irrelevance or lack of comprehensibility or acceptability;
- items with poorer discrimination (>70% selecting the lowest or highest category);
- redundant items (item to own-scale Cronbach's alpha of 0.8, corrected for overlap); and
- items measuring a construct other than that intended (component loadings <0.4 in principal components analysis).

Items meeting the above criteria will be discussed with [name] before a final decision on removal.

Factor analysis

Confirmatory factor analytic techniques will be used to test the goodness of fit of the two-factor solution for the FS-ICU developed in the North American validation study.⁸

Reliability analysis

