Variation in family satisfaction by: family member characteristics (e.g. relationship to the patient); patient/admission characteristics; unit/hospital characteristics; and other contextual factors will be explored using multilevel linear regression modelling. The outcomes for the regression models will be the two domain scores for satisfaction with care and satisfaction with decision-making. Models will be stratified by the survival status of the patient at discharge from the critical care unit. The levels of the model will be: level 1, family member; level 2, patient/critical care unit admission; level 3, unit/hospital. Family member characteristics entered into the models will include: age; sex; and relationship to the patient. Patient/admission characteristics will include: age; sex; severe chronic conditions in the past medical history; surgical status (elective surgery, emergency surgery, non-surgical); acute severity of illness (ICNARC Physiology Score¹⁹); and length of stay in the critical

care unit. Unit/hospital characteristics will include: teaching status; and number of beds in the critical care unit. Contextual factors will include: month of the year (seasonality). Non-linearity in the relationship between continuous predictors and satisfaction will be modelled using restricted cubic splines.

Variation in family satisfaction by country will be explored by comparing data collected for the FREE study with FS-ICU data from Canada (and available to [name]) in the context of a multilevel linear regression model with a similar structure to that above. Country comparisons will be adjusted for the age, sex and relationship to the patient of the family member and for patient characteristics consistently recorded in the different datasets.

As routinely surveying family members of all patients admitted to a critical care unit would neither be feasible nor cost-effective, understanding the association between patient factors and family satisfaction will enable an appropriately stratified sampling frame to be explored and developed.

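### The UK–Canada comparison cannot separate country from questionnaire version, and the version behind the Canadian data is not stated

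*Protocol*

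**What the plan says.** Comparison by country is a listed objective (Protocol, sections 1 and 3). Section 7.2, Main analysis, sets out the method: "Variation in family satisfaction by country will be explored by comparing data collected for the FREE study with FS-ICU data from Canada". The model is a multilevel linear regression built like the main one, whose outcomes are the care and decision-making domain scores. It adjusts for the respondent's age, sex and tie to the patient, and for patient characteristics recorded alike in the datasets. No questionnaire version is named for the Canadian data, and no rule restricts scoring to shared items.

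On the UK side, section 4 says the cohort will "address the remaining objectives using the UK adaptation of the FS-ICU questionnaire (FREE-Qual"). That adaptation can differ from its source in three ways:

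- **Wording.** Section 5.2.1 has the team "render into UK English any words or items that require 'translation", with the developer advising on semantic equivalence. Section 5.2.2 allows rewording after each round of cognitive interviews.
- **Items at the qualitative stage.** Under section 5.2.3, findings may "suggest that one or more items from the FS-ICU should be dropped". If content is missing, "appropriate items (with the same response format as existing FS-ICU items) will be drafted and tested through further cognitive interviews with family members".
- **Items after the first month.** Section 7.2 states: "The following criteria will be used to tag items for possible removal". Substantive changes would lead to a new version and a fresh 12-month recruitment period.

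Section 2 sets the general principle that "an instrument developed and validated in one place cannot simply be used in another without careful cross-cultural adaptation". It also records that the FS-ICU went from 34 to 24 items in 2007.

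**The concern.** A difference in mean domain score between two countries can be read as a difference in satisfaction only if equally satisfied families would score the same in both. Here the UK form is used only in the UK. Whatever effect its wording or item set has on the score moves with country and cannot be removed by adjusting for who responded or how ill the patient was. The Canadian side adds its own uncertainty: the two Canadian studies cited in section 2 date from 2001 and 2002, before the 2007 reduction, and section 7.2 does not say whether the Canadian data come from the longer or the shorter form.

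At stake is what the country objective can conclude. A coefficient labelled as country could contain an instrument component of unknown size, and a large UK sample does not shrink it.

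**Working it through.** **1. The plan's own figures.** The Protocol gives no figure for the country comparison. The only calculation on the domain-score scale is the power statement in section 7.1: SD 20, difference 4, a factor present in 10% of patients, p<0.01 (taken as two-sided), power above 90%. Counting each patient once:

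- 5,500 patients: SE = 20 × √(1/550 + 1/4,950) = 0.90; 4/0.90 − 2.58 ≈ 1.87; power 97.0%.
- 6,700 patients: SE = 20 × √(1/670 + 1/6,030) = 0.81; 4/0.81 − 2.58 ≈ 2.34; power 99.0%.

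Both statements reproduce, and the point below does not touch them.

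**2. Why adjustment cannot help.** Write the expected score as μ + βC + δV + γx, where C marks the UK, V marks the UK form and x holds the respondent and patient covariates. Every UK response has C = V = 1 and every Canadian response has C = V = 0. The two columns are identical, so only β + δ can be estimated. If the forms are equivalent, δ is 0 and there is no harm. The stated analysis contains nothing that tests this.

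**3. What the planned checks can show.** The confirmatory factor analysis in section 7.2 tests whether the North American two-factor solution fits. Good fit supports a similar structure. It does not show equal item thresholds or intercepts across countries, which a comparison of means needs. The developer's review in sections 5.2.1 and 5.2.2 is expert judgement on meaning, not a test of score equivalence.

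**4. Has the scored item set changed?** Counting Appendix 1:

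- care: Q1, Q2a–c and Q3–Q12, so 1 + 3 + 10 = 14;
- decision-making: Q1–Q10, so 10;
- total 24.

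This matches the 24 items for which section 7.2 writes the main analysis. (Q11–Q13 on dying patients and the closed item Q14 stand outside this count.) On the current text, dropped or added items are a contingency.

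**5. Illustrative size.** Assume a domain score is the mean of K items on a 0–100 scale. Removing one item that lies g points below the K-item mean raises the score by g/(K − 1). An item above the mean lowers it by the same amount. The values of g are assumptions; the documents give none.

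| Domain | K | g = 10 | g = 20 |
|---|---|---|---|
| Care | 14 | 10/13 = 0.77 | 20/13 = 1.54 |
| Decision-making | 10 | 10/9 = 1.11 | 20/9 = 2.22 |

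If the other country's score keeps the item, this shift passes in full into the country coefficient. Scoring both countries on the same items removes it.

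**6. Direction.** One removal criterion in section 7.2 tags items with more than 70% of answers in an extreme category. Suppose 70% score 100 and the rest average 50 to 75 (assumed). The item mean is then 70 + 0.3 × 50 = 85 up to 70 + 0.3 × 75 = 92.5, against the anticipated domain mean of 80. Dropping such an item lowers the score by 5/9 to 12.5/9 = 0.6 to 1.4 points (10 items) or 5/13 to 12.5/13 = 0.4 to 1.0 points (14 items). An item with a low mean would work the other way, so no direction can be presumed.

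**The case against.** The strongest reply is that this is analysis-plan detail. The Protocol names the data, the model and the adjustment set, calls the comparison exploratory, and prevents nobody from rescoring on common items or testing invariance. That limits the weight of the point. It does not dispose of it, because the Protocol itself fixes the outcome and the adjustment, and the method as stated cannot separate the two effects.

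The safeguards also deserve credit. Rewording starts from words that need translation, the developer advises on equivalence, interviewees' readings are checked against intended meaning, the North American scoring algorithm is used (stated for the psychometric stage), and removal of an item is discussed first. These make a large instrument effect less likely. None of them measures it.

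Four stronger readings are tempting, and the documents do not support them:

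- **That the UK scale has been shortened or extended.** Section 7.2 and Appendix 1 both point to 24 items. The month-one criteria concern removal only.
- **That the plan contradicts its own background.** Section 2 asks for adaptation and psychometric checking, and its examples of minimum standards include replication of the factor structure, which the plan tests. Equality of item thresholds is a statistical requirement for comparing means, not one that section 2 states.
- **That the possible bias is about half of a difference the study calls meaningful.** The 4 points in section 7.1 are a detectable difference for a patient factor. Section 2 says that what counts as a meaningful difference still has to be understood.
- **That the bias is known to favour one country.** Step 6 of the working shows that it could go either way.

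**Conclusion.** The point holds in a limited form. Because the UK adaptation is used only in the UK and the Canadian version is unnamed, country and instrument version are aliased in the model described in section 7.2. Neither the two-factor test nor the developer's review shows that equal scores mean equal satisfaction in both countries.

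The size and direction of any bias cannot be derived from the documents. The range of about 0.8 to 2.2 points, either way, is an illustration that rests on three assumptions: a domain score that is a simple item mean, one item not common to both scores, and an item gap of 10 to 20 points. The effect of rewording alone cannot be sized at all. The power statements and the within-UK analyses are unaffected. This is an inexpensive improvement to an exploratory comparison, not an error that undermines the study.

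**What to change.** In the country-comparison paragraph of section 7.2:

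1. State which FS-ICU version produced the Canadian data.
2. Score both countries with the same algorithm on the items common to both versions.
3. As a sensitivity analysis, fit a two-group confirmatory factor model with loadings and thresholds constrained equal, or run item-level differential item functioning tests. Report the country difference on the invariant items alongside the all-item difference.
4. If item-level Canadian data are not available, state that country and questionnaire version cannot be separated, and word the result accordingly.

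The cost is one extra model and possibly a slightly shorter score for this comparison. No new data collection is needed, but steps 2 and 3 depend on item-level Canadian data, and section 7.2 speaks only of FS-ICU data. One limit remains: these checks find items that behave differently from the rest. A shift common to every item would still look like a country difference, and the report should say so.

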A number of potential alternative sampling frames will be constructed based on results of the regression models, and varying the numbers of patients sampled and the timing(s) of the samples within the year. Potential sampling frames include: 100% sampling over a short timeframe; simple random sampling; and random sampling stratified by patient/admission characteristics (e.g. age, sex, survival status, length of stay). The representativeness of the proposed sampling frames will be assessed by assessing the correlation between the FS-ICU domain scores calculated in the sample and in the total population for each critical care unit. Uncertainty in the correlation will be assessed using bootstrapping techniques.

8. Ethical compliance

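### If a short sampling window is recommended because it scored best, its correlation will be too high, and the planned bootstrap does not correct for the choice

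*Protocol*

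**What the plan says.** The fourth objective in Protocol section 3 is "to model approaches to sampling to achieve representative sampling for feasible, cost effective future use of the FS-ICU". Section 7.2 gives the method at the end of the main analysis. Understanding how patient factors relate to satisfaction "will enable an appropriately stratified sampling frame to be explored and developed". Several alternative "sampling frames will be constructed based on results of the regression models", with variation also in the number of patients and in "the timing(s) of the samples within the year". Three types are listed: "100% sampling over a short timeframe; simple random sampling; and random sampling stratified by patient/admission characteristics".

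Representativeness is to be judged by the "correlation between the FS-ICU domain scores calculated in the sample and in the total population for each critical care unit". On precision, the section says: "Uncertainty in the correlation will be assessed using bootstrapping techniques".

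FS-ICU scores exist only for people who returned a questionnaire, so in practice the reference is the unit's score over all respondents of the recruitment year. Section 4 fixes the number of units at twenty. No other period, set of units or external data set is named for this step, and no rule is given for choosing among the frames.

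**The concern.** The aim is advice on future use, so what matters is how a frame would perform with other respondents in another year. The plan measures how well it performs on the respondents from whom it was drawn.

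That is harmless for a frame fixed in advance. It is not harmless for the winner of a comparison. A one-month window yields about 35 responses per unit, and its correlation rests on about 20 points, so the correlations of different months will scatter widely by chance. The highest of them belongs partly to the month whose noise happened to line up with that year's total. An interval bootstrapped around that one correlation takes the chosen window as given and leaves the choice out.

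At stake is the guidance to units: a window could be presented as unusually representative when any other month would do as well in the following year.

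**Working it through.** **The plan's own figure.** The document states no figure for the sampling-frame step. The nearest is the power of over 90% in section 7.1 for the patient-factor analysis. With 5,500 patients, a factor present in 10% (550 against 4,950), a difference of 4, SD 20 and two-sided p<0.01:

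- standard error = 20 × √(1/550 + 1/4,950) = 0.899
- 4/0.899 = 4.45; 4.45 − 2.576 = 1.874; power = 0.970.

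The figure reproduces with the patient as unit and no clustering. It says nothing about the comparison of frames.

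**Inputs from the protocol.** 20 units (section 4); 8,500 responses from 5,500 patients and SD 20 (section 7.1). Responses per unit-month = 8,500/(20 × 12) = 35.4. Responses per patient = 8,500/5,500 = 1.55.

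**Assumed inputs, not in the protocol.** The between-unit SD, the within-patient correlation, and no true seasonal effect. With a within-patient correlation of 0.5 the design effect is 1 + (1.55 − 1) × 0.5 = 1.27.

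**Simulation 1, twelve one-month windows.** Unit effects are normal with the assumed SD. Each monthly unit mean has error SD 20/√(35.4/design effect). For 4,000 simulated years per setting, each month's 20 unit means were correlated with the annual unit means, the best month was picked, and that month was scored again in an independent year. With design effect 1:

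| Between-unit SD | Average month | Best of 12 | Same month, next year | Excess |
|---|---|---|---|---|
| 2 | 0.56 | 0.77 | 0.56 | 0.21 |
| 3 | 0.69 | 0.84 | 0.69 | 0.15 |
| 4 | 0.78 | 0.89 | 0.78 | 0.11 |
| 5 | 0.84 | 0.92 | 0.84 | 0.08 |

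With design effect 1.27 the best month scores 0.75-0.90 and the same month next year 0.53-0.81, an excess of about 0.09-0.23.

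**Simulation 2, window length.** Individual responses were simulated with 276 patients per unit, one or two responses each and within-patient ICC 0.4. The unit ICC runs from 0.01 to 0.10, that is a between-unit SD of 20 × √ICC = 2.0 to 6.3. Cells show best window / same window in fresh respondents:

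| Unit ICC | 12 months | 4 quarters | 2 half-years |
|---|---|---|---|
| 0.01 | 0.750 / 0.526 | 0.847 / 0.762 | 0.914 / 0.898 |
| 0.02 | 0.810 / 0.630 | 0.896 / 0.841 | 0.946 / 0.937 |
| 0.05 | 0.888 / 0.785 | 0.948 / 0.923 | 0.975 / 0.972 |
| 0.10 | 0.934 / 0.874 | 0.972 / 0.958 | 0.987 / 0.986 |

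The excess is 0.06-0.22 for months, 0.01-0.09 for quarters and 0.02 or less for half-years.

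**Random frames.** One simple random and six stratified frames were compared at unit ICC 0.02, each averaged over 400 draws. The best scored 0.650 against 0.642 in fresh respondents with 23 patients per unit, and 0.850 against 0.846 with 69. The excess is under 0.01.

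**Does the bootstrap cover it?** With design effect 1.27 and between-unit SD 2-5, a 95% interval from resampling units covers the true average correlation about 90% of the time for a month not chosen on its score, but under 60% of the time for the best month.

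**What the excess is not.** A sample is part of the total it is compared with, and this raises every frame's correlation: at unit ICC 0.02 and within-patient ICC 0.3, an average month scores 0.64 against the full total but 0.56 against the other eleven months. The best window and its re-scored value share this overlap, so the excess above is selection alone.

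**The case against.** The strongest reply is that the protocol never says it will keep the highest correlation. It lists possible frames and assesses them, and feasibility and cost are aims too. Shown side by side, the correlations carry no winner's bias. This stands: the inflation is conditional on a recommendation that the document does not spell out. What keeps the point alive is that the step exists to inform future sampling, timing is one of the things varied, and the correlation is the only measure of representativeness given.

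A reader might also infer that building strata from the study's own regressions inflates the results. The document's frames do not support that. Two of the three types need no regression results, and for the stratified type the excess is under 0.01.

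It can be said that a short timeframe is undefined, so one-month windows are only one reading. This is also right, and is why quarters and half-years are shown. The problem shrinks quickly as windows lengthen.

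Section 7.2 puts month of the year into the multilevel models, so timing would not be judged by the correlation alone. That helps detect a real seasonal shift in the mean score. It does not adjust the correlation of a window that was picked for its correlation.

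Finally, hold-out and resampling details often belong in a statistical analysis plan, which is not shown and may supply them. The point therefore rests on what section 7.2 does fix: the criterion, the reference total and the stated role of the bootstrap.

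**Conclusion.** The point holds in conditional form. If a short window is recommended because it scored best, its reported correlation overstates what the same window would give with new respondents by about 0.06-0.23 for one-month windows, 0.01-0.09 for quarters and about 0.02 or less for half-years. The larger values belong to small between-unit variation (SD about 2 points), the smaller to SD 5-6. All assume no true seasonal effect and a between-unit variance that the document does not give.

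The document does not support saying that the plan will report an inflated result, nor that the regression-based strata are at fault. The main regression analyses are untouched. The correction is cheap and worth making, because the affected output is the practical advice on sampling.

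**What to change.** In section 7.2:

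- For frames that survey everyone over a short timeframe, report the mean and range of the correlation over all possible start times, not one window or the best one. Add that a wide range is not in itself evidence of a timing effect: in simulation 1, without seasonality, the best and worst months differ by 0.19-0.50.
- Recommend a specific timing only if its advantage is confirmed outside the data used to choose it, or with the choice repeated inside each bootstrap resample. One way to confirm it is to split patients at random within units, keeping all relatives of a patient together, choose in one half, score in the other, then swap and average.
- State that a split within one year cannot fully establish that the timing would reproduce in another year, since both halves share that year's circumstances.

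The cost is a little more programming on data already collected, with no effect on recruitment. Where halves are used, responses per unit-month fall from about 35 to about 18, so the reported correlation is lower and less precise. Reporting the mean and range over start times carries no such loss.
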